## **5. DESCRIPTION OF NON-STANDARD DATA COLLECTED AND DERIVED VARIABLES**

### **5.1 Other Non-Standard Baseline Characteristics**

The following non-standard baseline characteristics have been collected at screening:

- Test Report for H-pylori
- Upper GI Ultrasound
- Endoscopy
- 12 Lead Electrocardiogram
- Pregnancy Test

### **5.2 Non-Standard Disease History**

Not applicable.

### **5.3 Efficacy data**

The following efficacy endpoints data values are collected, and the required derivation is provided:

#### **5.3.1 Primary Efficacy Endpoint**

##### **▪ Symptoms of dyspepsia using Leeds Dyspepsia Questionnaire (LDQ)**

The Leeds Dyspepsia Questionnaire (LDQ) consists of 15 questions out of which only 8 questions will be used to determine the severity of dyspepsia.

The eight questions from 1-8 are given below:

1. *Over the last FOUR WEEKS have you had any indigestion (a pain in the upper abdomen)?*  
[Yes/No]
2. *Over the past FOUR WEEKS have you ever experienced heartburn (a burning feeling behind the breastbone)?*  
[Yes/No]
3. *Over the past FOUR WEEKS has food or drink ever stuck behind your breast bone as it went down?*  
[Yes/No]
4. *Over the last FOUR WEEKS have you experienced any regurgitation (an acid taste coming up into your mouth from your stomach)?*  
[Yes/No]
5. *Over the last FOUR WEEKS have you noticed excessive burping or belching?*

*[Yes/No]*

6. *Over the last FOUR WEEKS have you ever experienced any nausea (a feeling of sickness without actually being sick)?*

*[Yes/No]*

7. *Over the last FOUR WEEKS have you ever experienced any vomiting?*

*[Yes/No]*

8. *Over the last FOUR WEEKS have you noticed an excessive feeling of fullness after eating?*

*[Yes/No]*

All the eight questions have a Yes or No response.

The severity score of dyspepsia will be derived as follows:

Step 1:

If No is checked by a subject for any of the above 8 questions the zero severity score will be allocated to that question.

Step 2:

If Yes is checked by a subject for any of the above 8 questions, a further two additional questions will be asked.

For 1, 2, 4, 5, 6, 7, and 8 questions the two additional questions will be asked are as follows:

- (a) *How often have you had [the respective symptom] over the last FOUR WEEKS?*

*[1 = between once a month and once a week; 2 = more than once a week; 3 = at least one a day]*

- (b) *How severe has your [respective symptom] been over the last FOUR WEEKS?*

*[1 = very mild; 2 = mild; 3 = moderate; 4 = severe; 5 = very severe]*

Only question “(b)” will be used to determine the severity score.

Convert the categorical response of question b in numeric scores as follows:

Response	Score
Very Mild	1
Mild	2
Moderate	3
Severe	4
Very Severe	5

Hence, the possible severity score for the above questions is either 0 or (based on question b only) from 1 = very mild to 5 = very severe.

Step 3:

For the 3rd question, the two additional questions will be asked are as follows:

- (a) *How often does it stick behind your breastbone?*  
[1 = between once a month and once a week; 2 = more than once a week; 3 = at least one a day]
- (b) *How severe has your [respective symptom] been over the last FOUR WEEKS?*  
[1 = very mild; 2 = mild; 3 = moderate; 4 = severe; 5 = very severe]

Convert the categorical response of question a and b in numeric scores as follows:

Response	Score
Between once a month and once a week	1
More than once a week	2
At least once a day	3
Very Mild	1
Mild	2
Moderate	3
Severe	4
Very Severe	5

Both question (a) and (b) will be used to determine the severity score as follows:

Question 3 score = Score of (a) + Score of (b)

Hence, possible severity score for question 3 is either 0 or (based on sum of question a and b) 2 to 5.

Step 4:

The overall LDQ score will be obtained by summing all the 8 question's scores

Overall LDQ score

= Score of Q1 + Score of Q2 + Score of Q3 + Score of Q4 + Score of Q5 + Score of Q6 + Score of Q7 + Score of Q8

The following simulated example of patient's response and score calculation can be referred for better understanding of the scoring procedure:

Question No.	Response (Yes/No)	If Yes, Sub question (a)			If Yes, sub question (b)					Score
		1 = between once a month and once a week	2 = more than once a week	3 = at least one a day	Very Mild = 1	Mild = 2	Moderate = 3	Severe = 4	Very Severe = 5	
1	No	Ignore (a)			Ignore (b)					0
	Yes									
2	No	Ignore (a)								3
	Yes						3			
3	No									2+4 = 6
	Yes		2					4		
4	No	Ignore (a)								1
	Yes				1					
5	No	Ignore (a)								3
	Yes								3	
6	No	Ignore (a)								2
	Yes					2				
7	No	Ignore (a)			Ignore (b)					0
	Yes									
8	No	Ignore (a)								5
	Yes									
Overall LDQ Severity Score										20 = [ 0 + 3 + 6 + 1 + 3 + 2 + 0 + 5]

Note 1: The above table calculation is simulated to better understanding of the scoring procedure.

Note 2: The grey shaded shells indicating the response of patient for that particular question.

### 5.3.2 Secondary Efficacy Endpoints

#### ▪ Quality of Life assessment using Short Form - Nepean Dyspepsia Index (SF-NDI)

The SF-NDI is composed of two parts:

##### Part 1:

##### Functional Dyspepsia by SF-NDI Symptoms

Step 1:

There are 15 symptoms (items) that measure frequency by evaluating “How OFTEN did you have it?”, intensity by evaluating “If you had this problem, how INTENSE was it usually?” and bothersomeness by evaluating “If you had this problem, how BOTHERSOME was it?” to establish a symptom score.

Out of 15 symptoms only the following 4 symptoms will be used to calculate the score of functional dyspepsia by NDI.

- *Pain or ache in upper abdomen*
- *Burning sensation in upper abdomen PDS:*
- *Inability to finish a regular meal*
- *Fullness after eating or slow digestion*

Convert the responses of frequency, intensity and bothersomeness into numeric scores as follows:

Frequency How OFTEN did you have it?		Intensity “If you had this problem, how INTENSE was it usually?”		Bothersomeness “If you had this problem, how BOTHERSOME was it?”	
Not at all	0	Not at all	0	Not at all	0
One to four days	1	Very mild	1	A little bit	1
Five to eight days	2	mild	2	Moderately	2
Nine to twelve days	3	Moderate	3	Quite a bit	3
Every day/Almost every day	4	Severe	4	Extremely	4
		Very Severe	5		

**Step 2:**

Calculate each symptom score as follows:

Symptom score = Frequency score + Intensity score+ Botheromeness score

**Step 3:**

Calculate the Functional Dyspepsia score as follows:

Functional Dyspepsia score = sum of all 4 symptom (*Pain or ache in upper abdomen + Burning sensation in upper abdomen PDS + Inability to finish a regular meal + Fullness after eating or slow digestion*) score

**Part 2:**

**QoL**

The SF-NDI is composed of 10 QoL items investigating 5 domains.

**Transformation for Raw Score,**

**Step 1:**

Convert the responses of QoL items into numeric scores as follows:

Response of QoL items	Score
Not at all	1
Not applicable	1
Almost Never	1
A little	2
Sometimes	2
Moderately	3
Fairly often	3
Quite a lot	4
Very often	4
Extremely	5
Always	5

**Step 2:**

Categorize the five domains as follows (categorized in CRF as well):

Domain	Number of Items	Cluster of Items
Tension	2	1, 2
Interference with daily activities	2	3, 4
Eating/Drinking	2	5, 6
Knowledge/Control	2	7, 8
Work/Study	2	9, 10

Step 3:

Calculate the score of each domain as follows:

Tension = Score of 1 + Score of 2; similarly for each domain.

Step 4:

The overall total score is obtained by using the mean of the 5 subscale/domain total scores

Overall QoL Raw Score

=

Raw scores for (Tension + Interference with daily activities + Eating/Drinking + knowledge/Control + Work/Study) ÷ 5

### Transformation for Standardized Score,

Convert the responses of QoL items into numeric scores as per step 1 and categorize the five domains as per step 2 defined above for transformation of raw score.

Step 3:

Calculate the score of each domain as follows:

Tension = Score of 1 + Score of 2; similarly for each domain.

Step 4:

Transform the domain scores as follows:

*Transformed Scale Score*

$$= 100 - \left[ \frac{(\text{Actual Raw Score} - \text{Minimum Possible Score})}{\text{Range}} \times 100 \right]$$

Where,

*Minimum Possible Score = 2*

*Range = (Maximum Possible Score – Minimum Possible Score) = (10 – 2) = 8*

Note:

Each item is scored on likert scale and converted into numeric scores as per step 1. Each domain is measured using 2 questions as per step 2.

Step 5:

overall SF-NDI total score is obtained by mean of 5 domain score as follows:

Overall QoL Transformed Score

=

Transformed scores for (Tension + Interference with daily activities + Eating/Drinking + knowledge/Control + Work/Study) ÷ 5

The following simulated example of patient's response and score calculation can be referred for better understanding of the scoring procedure:

Question No.	Response	Converted Response Into Numeric Score	Categorization of Domains	Score for each domain	Transformed Scale Score
1	QUITE A LOT	4	Tension	$4 + 3 = 7$	$\frac{(7 - 2)}{8} \times 100 = 62.5$
2	MODERATELY	3			
3	EXTREMELY	5	Interference with daily activities	$5 + 4 = 9$	$\frac{(9 - 2)}{8} \times 100 = 87.5$
4	QUITE A LOT	4			
5	MODERATELY	3	Eating/Drinking	$3 + 4 = 7$	$\frac{(7 - 2)}{8} \times 100 = 62.5$
6	QUITE A LOT	4			
7	FAIRLY OFTEN	3	knowledge/Control	$3 + 5 = 8$	$\frac{(8 - 2)}{8} \times 100 = 75.0$
8	ALWAYS	5			
9	QUITE A LOT	4	Work/Study	$4 + 3 = 7$	$\frac{(7 - 2)}{8} \times 100 = 62.5$
10	MODERATELY	3			

Overall QoL Transformed Score	$(62.5 + 87.5 + 62.5 + 75.0 + 62.5) \div 5 = 70.0$
-------------------------------	--

▪ **Symptoms of dyspepsia assessed by Numerical Rating Scale (NRS 11)**

Convert each NRS 11 responses into numeric score as follows:

Symptom response	Score
No	0
Very Mild	1
Discomforting	2
Tolerable	3
Distressing	4
Very distressing	5
Intense	6
Very Intense	7
Horrible	8
Unbearable	9
Unspeakable	10

Each symptom will be analyzed separately according to symptom score.

▪ **Responders for adequate/satisfactory relief as assessed**

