### ▪ **Disease Specific Quality of Life (Nepean Dyspepsia Index NDI) assessed at baseline and week 8**

The Short Form Nepean Dyspepsia Index (SF-NDI) is composed of 10 QoL items investigating 5 domains. There are also an additional 15 items that measure frequency, intensity and bothersomeness. The symptom score can be modified to assess role functional dyspepsia score. The values of overall QoL score, QoL domain score, and functional dyspepsia score will be derived as per [section 5.3.2](#)

All 15 symptoms/items that measure frequency, intensity and bothersomeness will be summarized descriptively, using frequency count (n) and percentages by Test group and Active Control group for baseline and week 8.

All 15 symptoms/items will be converted to symptom scores by summing the values of frequency, intensity and bothersomeness for each symptom will be analyzed by using the number of non-missing observations (n), mean, standard deviation (SD), median, minimum (Min) and maximum (Max) by Test group and Active Control group for baseline and week 8.

Functional Dyspepsia score modified by specific symptom scores described in [section 5.3.2](#) will be analyzed by using the number of non-missing observations (n), mean, standard deviation (SD), median, minimum (Min) and maximum (Max) by Test group and Active Control group for baseline and week 8.

Each QoL domain/subscale raw scores and transformed scale scores as described in [section 5.3.2](#) and their overall scores will be summarized by using the number of non-missing observations (n), mean, standard deviation (SD), median, minimum (Min) and maximum (Max) by Test group and Active Control group for baseline and week 8.

A two sample t-test will be used to check the significance difference between Test group and Active Control group at 5% level of significance.

The above analysis will be performed for Full Analysis (FA) subject sample.

▪ **Change from baseline of NRS 11 score for symptoms after week 4 and week 8**

The patient is provided with the NRS 11 scale to mark changes for symptoms of sensation of bloating, early satiety, postprandial fullness, upper abdominal pain, or discomfort (epigastric pain, epigastric burning), anorexia (loss of appetite), heartburn, nausea, and vomiting.

The NRS scale scores for each symptom will be obtained as per [section 5.3.2](#).

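### The SF-NDI transformed-score formula and its worked example run in opposite directions: the same patient scores 30.0 by the formula and 70.0 in the example

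*SAP*

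**What the plan says.** SAP 5.3.2 codes each of the ten quality-of-life items from 1 (not at all) to 5 (extremely or always), so a higher item score means more impairment. Two items are added per domain: "Tension = Score of 1 + Score of 2; similarly for each domain". Under the standardized-score transformation, Step 4 then computes "100 - \left[ \frac{(\text{Actual Raw Score} - \text{Minimum Possible Score})}{\text{Range}} \times 100", closing the bracket there, with "Minimum Possible Score = 2" and a range of 10 - 2 = 8. For Step 5, "overall SF-NDI total score is obtained by mean of 5 domain score as follows".

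The same subsection then offers a "simulated example of patient's response and score calculation can be referred for better understanding of the scoring procedure". Its five domain cells show (raw - 2)/8 x 100 with nothing subtracted from 100, and its last line is "62.5 + 87.5 + 62.5 + 75.0 + 62.5) \div 5 = 70.0".

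On analysis, SAP 4.2.2 summarises raw and transformed scores by arm at baseline and week 8 and adds: "A two sample t-test will be used to check the significance difference between Test group and Active Control group at 5% level of significance". SAP 4.7 repeats the analysis in subgroups. In SAP 9.3.1 the overall transformed-score table, 10.1.2.2.3.5, is marked for headline results. SAP 7.2 records that the derivation of the transformed score is new in this SAP version.

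**The concern.** The SAP gives two complete scoring rules for one secondary endpoint, and each is the mirror image of the other. Under Step 4, 100 is the least impaired state and 0 the most impaired. Under the example, 0 is the least impaired and 100 the most. No sentence in the protocol or SAP says whether a higher transformed score is good or bad, and the footnotes in the table shells cover only the definition of baseline and the t-test.

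The shell of Table 10.1.2.2.3.5 prints each arm's mean, SD, median, range and a p-value at each visit. A reader must therefore judge which arm did better, and whether patients improved, from which mean is higher. If the wrong rule is programmed, that judgement is reversed. If the production programmer follows the formula and the QC programmer the example, they will disagree on every score except exactly 50.

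**Working it through.** **Inputs, all from SAP 5.3.2.** Item scores in the example: 4, 3, 5, 4, 3, 4, 3, 5, 4, 3. These agree with the item coding table. Minimum domain score 2, range 8, overall score = mean of the five domains.

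**Rule A, Step 4 as written:** 100 - (raw - 2)/8 x 100.
**Rule B, as shown in the example:** (raw - 2)/8 x 100.

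| Domain | Raw | Rule B (printed in the SAP) | Rule A (Step 4) |
|---|---|---|---|
| Tension | 4 + 3 = 7 | 5/8 x 100 = 62.5 | 100 - 62.5 = 37.5 |
| Interference with daily activities | 5 + 4 = 9 | 7/8 x 100 = 87.5 | 100 - 87.5 = 12.5 |
| Eating/Drinking | 3 + 4 = 7 | 62.5 | 37.5 |
| Knowledge/Control | 3 + 5 = 8 | 6/8 x 100 = 75.0 | 100 - 75.0 = 25.0 |
| Work/Study | 4 + 3 = 7 | 62.5 | 37.5 |
| Sum | | 350.0 | 150.0 |
| Overall (sum / 5) | | **70.0** | **30.0** |

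Rule B reproduces the SAP's 70.0 exactly, so that figure is correct arithmetic on a formula other than the one the SAP defines. Because all five cells and the total agree with Rule B, this is neither an isolated slip nor a fault of text extraction.

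**At the extremes.** Raw 2 (no impairment) gives 100 by Rule A and 0 by Rule B. Raw 10 gives 0 by Rule A and 100 by Rule B.

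**Effect on the analysis.** Replacing x by 100 - x turns each mean m into 100 - m and leaves the SD unchanged. A between-arm difference m1 - m2 becomes (100 - m1) - (100 - m2) = -(m1 - m2), so the size and standard error stay the same and the sign flips. Changes from baseline flip sign in the same way. A check on simulated data (250 per arm, means 40 and 45, SD 20; illustrative values, not from the trial documents) moved t from -4.599 to +4.599 and left the two-sided p-value at 5.39e-06.

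**Where the score appears.** Tables 10.1.2.2.3.5 (overall, headline) and 10.1.2.2.3.6 to 10.1.2.2.3.8 (subgroups, not headline), and Listing 12.2.6.3.2, which includes change from baseline. The raw-score tables use neither rule.

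**The case against.** The strongest reply is that the formula is the stated derivation and the example only illustrates it, so the ordinary reading is that Step 4 governs and the example is wrong. That is the more natural reading, and it means a reversed report is a risk, not the plan's default result. But the SAP states no precedence, it directs readers to the example to understand the scoring, and an example with printed answers is what a programmer would naturally validate against.

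A second reply is that a reversal would be noticed. Raw scores are tabulated for the same sample, domains and visits, and raw and transformed values sit side by side in Listing 12.2.6.3.2. Under Step 4 they should move in opposite directions. This also stands in part: a reversal is detectable, but the SAP neither requires the comparison nor says which direction to expect.

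A reader might infer more than the documents support:

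- **That both headline quality-of-life tables are exposed.** Table 10.1.2.2.3.1 reports raw scores, whose derivation contains no conflict. Only 10.1.2.2.3.5 is affected.
- **That a printed treatment effect changes sign.** The transformed-score shells have no change-from-baseline row and no between-arm difference. Signed changes appear only in the listing; in the tables, the reversal is in how the means are read.
- **That significance or trial success is at stake.** The two-sided p-value is the same under either rule. Success rests on the LDQ, and no responder rule or threshold uses this score.

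**Conclusion.** The contradiction is certain and can be checked by hand: 30.0 by the formula against 70.0 in the example, for the same patient, within one subsection. For that patient the gap is 40 points on a 100-point scale; in general it is |100 - 2x|, up to 100 points at the extremes. Following the example would reverse the apparent direction of change and the apparently better arm in one headline table, three subgroup tables and the change values of one listing.

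The consequence is confined to the level and direction of one secondary score. SDs, absolute differences, two-sided p-values, the raw-score tables, the primary LDQ analysis and the sample size are unaffected. The p-value statement takes the planned t-test as two-sided, which the SAP does not spell out. Which direction the instrument's own manual uses cannot be settled from these documents; the finding does not depend on it, because the SAP contradicts itself either way. It should be resolved before the derivation is programmed and validated.

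**What to change.** Keep one rule. Confirm the direction against the instrument's scoring manual. If it agrees with Step 4, retain the formula and correct the example to show the subtraction from 100 in each domain cell, giving 37.5, 12.5, 37.5, 25.0 and 37.5, overall 30.0. If the manual runs the other way, change the formula instead and leave the example.

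State the direction in words (under Step 4: 0 = worst, 100 = best quality of life) in SAP 5.3.2 and in the footnotes of Tables 10.1.2.2.3.5 to 10.1.2.2.3.8 and Listing 12.2.6.3.2. While editing, align the shell title of Table 10.1.2.2.3.8, which refers to the raw score, with the table list in SAP 9.3.1, which refers to the transformed score.

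The cost is SAP wording only; data collection, sample size and the choice of test do not change.

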**By LDQ Score:**

The subject is considered to be as responder if, at the end of the treatment the overall LDQ score is < 9.

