## **5 SELECTION OF STUDY POPULATION**

### **5.1 Inclusion Criteria**

1. Adult male and/or non-pregnant non-lactating female subjects aged above 18 years.
2. Subjects provided written informed consent and are willing to participate in the study.
3. Subjects with functional (non-ulcer) dyspepsia according to Rome IV criteria including postprandial distress syndrome (PDS) and with or without EPS (epigastric pain syndrome) with one or more of the following:
  - bothersome postprandial fullness,
  - bothersome early satiation
  - bothersome epigastric pain,
  - bothersome epigastric burning
  - for at least 12 weeks in the preceding 6 months
4. No evidence of organic, systemic, metabolic or structural disease likely to explain symptoms - Subjects who have to undergo physical examination and lab tests (including white-cell and red-cell counts, measurement of fasting blood sugar and liver-function tests), abdominal ultrasonography, and upper GI endoscopy\* in order to rule out structural cause for symptoms of FD.  
\*history of upper GI endoscopy within 6 months prior to enrolment or at screening.
5. Baseline severity of at least moderate symptoms on LDQ (total score  $\geq 9$ ) at screening.
6. H. pylori negative documented test report within 3 months prior to enrolment or during screening.

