### 8.1 Efficacy Measurements

- **Symptoms of dyspepsia using Leeds Dyspepsia Questionnaire (LDQ)**
- LDQ Questionnaire will be completed by the site staff through interview with patient by site staff trained on administration of LDQ to capture the overall symptomatology at screening (visit 1), week 4 (visit 3) and on week 8 (visit 4). The symptoms of dyspepsia are evaluated by measuring its frequency using the LDQ questionnaire which is a fully validated instrument to assess the symptoms of dyspepsia. A dyspepsia questionnaire or Leeds Dyspepsia Questionnaire (LDQ) can identify subjects with dyspepsia by measuring its frequency and therefore will assess the severity via a calculated overall score

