## 10.1 General Definitions and Conventions

### Time-Related Definitions

All assessment dates will be related to the first day of study drug administration. This first day of drug administration is referred to as Day 1. Day –1 is the day that is preceding Day 1 and a Day 0 will not be defined.

The baseline period will be defined as the period from informed consent to the first study drug administration. The baseline value for a variable is defined as the last non-missing value collected before first study drug administration.

The endpoint value for efficacy variables is defined as the last non-missing value assigned to treatment for the subject.

All variables planned to be measured at one or more time points and supposed to be time-related will be windowed.

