The actual scores and change in scores from baseline for each symptom will be summarized using the number of non-missing observations (n), mean, standard deviation (SD), median, minimum (Min) and maximum (Max) by Test group and Active Control group for baseline and week 8.

The change in symptoms score will be analyzed by using analysis of covariance (ANCOVA) model. The model will include change in Symptom Score as dependent variable and treatment group, site, and Symptom baseline score as covariates. Two-sided 95% confidence intervals will be constructed for the least square mean (LS Mean) differences between Test group and Active Control group.

The above analysis will be performed for Full Analysis (FA) subject sample.

▪ **Responder Analysis of Satisfactory relief assessed by LDQ and NRS 11**

Based on the LDQ score, at the end of the study treatment subjects will be categorized into responders and non-responders (refer section 5.3).

Number of responders and non-responders will be summarized descriptively by using frequency count (n) and percentages (%) by Test Arm and Active Control Arm.

To check the significant difference between two treatment arms a chi-square test will be used when the normal approximation to the binomial is valid. Otherwise, a Fisher's exact test will be used if >20% of expected cell counts are less than 5.

Similarly, based on the NRS11 score, study treatment subjects will be categorized into responders and non-responders for each symptom (refer [section 5.3.2](#)) and similar analysis specified above will be performed.

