**By NRS-11 Score:**

The subject is considered to be as responder if, each NRS11 symptoms change from baseline score at the end of the study treatment is at least 2 (i.e., NRS-11 symptoms CFB  $\geq -2$ ). only subjects with a score of the respective symptom of at least 5 at baseline will be used.

▪ **Treatment acceptance and ease of use assessed by Likert Scale**

Convert the responses of treatment acceptance into numeric score as follows and analyze the scores:

Acceptance response	Score
Not at all satisfied	1
Slightly satisfied	2
Neutral	3
Very satisfied	4
Extremely satisfied	5

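### The LDQ responder cut-off (<9) mirrors the entry cut-off (≥9), so baseline LDQ strongly affects who responds, yet the arms are compared by an unadjusted test with a p-value only

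*SAP*

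**What the plan says.** Protocol 5.1, inclusion criterion 5, asks for "Baseline severity of at least moderate symptoms on LDQ", defined as a total score of at least 9 at screening. Under Protocol 8.1 and the flow chart in 8.6, the LDQ is taken at screening, week 4 and week 8, and not at visit 2. Protocol 10.1 adds: "The baseline value for a variable is defined as the last non-missing value collected before first study drug administration". The score that admits a subject is therefore normally also the LDQ baseline.

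SAP 5.3.2 defines the LDQ responder: "The subject is considered to be as responder if, at the end of the treatment the overall LDQ score is < 9". The notes to Tables 10.1.2.2.5.1 and 10.1.2.2.5.2 repeat this. No minimum change and no second visit are required. The neighbouring NRS 11 rule does ask for a change of at least 2, and "only subjects with a score of the respective symptom of at least 5 at baseline will be used".

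For the analysis, SAP 4.2.2 states: "Based on the LDQ score, at the end of the study treatment subjects will be categorized into responders and non-responders". Counts and percentages are then compared by chi-square, or by Fisher's exact test when expected counts are small. The table shells hold n (%) and a p-value. They have no difference, no confidence interval and no baseline term.

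**The concern.** Entry and response sit on opposite sides of the same number. A subject who goes from 9 to 8 is a responder, although one point is 1/7 = 0.14 of the plan's SD of change and less than the 1.75 margin. A subject who goes from 30 to 9 is not. How far a subject starts above 9 therefore matters a great deal, and selecting on a single reading invites some regression to the mean.

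The number of responders is a named secondary objective, and Table 10.1.2.2.5.1 is marked for the headline results. A test for a difference that ignores the main predictor and ends in a p-value gives the reader no estimate. If the p-value is non-significant, it may be taken as evidence that the two formulations are alike.

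**Working it through.** **1. The plan's own figure.** The only stated figure that uses LDQ variability is the primary sample size (Protocol 10.7: margin 1.75, SD 7, one-sided 2.5%, power 80%). Taking a true difference of 0, which is not stated, n = 2 × (1.960 + 0.842)² × 7² / 1.75² ≈ 251.2, so 252 per arm. The t-based version gives 253. Then 253/0.9 = 281.1, so 282 per arm and 564 in total. The plan's figures reproduce. No responder rate or responder power is stated.

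**2. Dependence on baseline.** With no mean change and integer scores, P(week 8 ≤ 8 | baseline b) = Φ((8.5 − b)/SD).

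| Baseline | 9 | 12 | 14 | 16 | 20 |
|---|---|---|---|---|---|
| SD 7 | 47% | 31% | 22% | 14% | 5% |
| SD 3.5 | 44% | 16% | 6% | 2% | 0.1% |

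SD 7 is an upper bound for noise, because the SD of change in treated subjects also contains real differences in response.

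**3. Responders with no true change, including regression to the mean.** Model: a stable true score with between-subject SD 4 or 6; independent visit error with SD = SD of change/√2 (7/√2 = 4.95); scores rounded and held within 0-43; entry if screening ≥9; response if week 8 <9. The population mean is set to give the stated enrolled baseline mean. Each range spans the two between-subject SDs.

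| SD of change | Enrolled mean 14 | Mean 17 | Mean 20 |
|---|---|---|---|
| 7 | 32-36% | 11-16% | 4-7% |
| 5 | 19-24% | 5-9% | 1-4% |
| 3.5 | 11-16% | 3-6% | 1-2% |

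**4. Check against the planned screening yield.** The plan expects 564 of about 700 screened, or 81%, to pass all criteria. The mean-14, SD-7 cells need an unselected mean of 6.4-9.6, so only 39-57% would pass the LDQ criterion alone. At SD 7, the scenarios with at least 81% LDQ-eligible are mean 17 with between-subject SD 4 (11%) and mean 20 (4-7%). Taking the mean-17 and mean-20 columns at all three SDs gives roughly 1-16%. The top of that range, at mean 17 with between-subject SD 6, falls somewhat short of the planned yield.

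A second model (unselected mean 11.6-17, SD 5-7, test-retest correlation 0.5-0.85) gives 2-22%. Its 22% case has Φ((11.6 − 8.5)/7) = 67% passing the LDQ criterion. The cases with an unselected mean of 14 or 17, where at least Φ((14 − 8.5)/7) = 78% pass, give 2-15%.

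**5. What baseline explains.** In the step 3 model with a real improvement added (6 points in one arm, 4.25 in the other), baseline LDQ explains about 4-41% of the variance of responder status, depending on scenario.

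**6. Would a stricter rule do better?** At SD 7 with no true change, requiring <9 at both week 4 and week 8 plus a fall of at least 5 lowers the rates to 12-16%, 2-5% and 0.5-1.5% for means 14, 17 and 20. The expected z for the real difference in step 5 (253 per arm, week-4 effect 70% of week 8, SD 7) is:

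| Enrolled mean | <9 at week 8 | Stricter rule |
|---|---|---|
| 14 | 2.2-2.5 | 2.2-2.5 |
| 17-20 | 1.9-2.5 | 1.3-2.0 |

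The stricter rule has fewer noise responders but is no more sensitive, and at the higher means it is less so.

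**The case against.** Falling below the protocol's own line for at least moderate symptoms is a coherent symptom-state endpoint. Size of change is already covered by the baseline-adjusted primary ANCOVA and by the NRS 11 rule. The LDQ rule does not lack a baseline floor either: eligibility supplies it, whereas NRS 11 has no entry threshold and needs its own. Four-week recall over eight items damps noise. The responder test lies outside the success rule and carries no non-inferiority claim. All of this stands, and it is why the definition need not change.

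A reader might infer that about a third of subjects become responders by noise alone. The documents do not support that. The 32-36% cells treat the whole SD of 7 as error, which implies a reliability of 0.40 or 0.60, and they conflict with the planned screening yield. In those cells 21-31% of enrolled subjects have a true score below 8.5, so many of the apparent noise responders would be classified correctly.

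A reader might also infer that the <9 rule should be replaced. Step 6 argues against that. A rule that keeps <9 and adds hurdles still counts 30 to 9 as failure, and it turns an end-of-treatment endpoint into a sustained-response one.

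These arguments do not defend the unadjusted test. Baseline LDQ is collected, is already in the primary model and predicts the outcome, so there is no reason to leave it out or to omit the estimate.

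**Conclusion.** The concern holds for the comparison and does not require a new responder definition. The shared cut-off makes response depend strongly on baseline LDQ and lets some subjects near 9 respond without true change: roughly 1-16% of enrolled subjects in scenarios closer to the planned screening yield. That size rests on assumed baseline means, between-subject SDs and reliability. It also treats the model's unselected population as the screened one, and assumes that the screening total is scored as in SAP 5.3.1, since the protocol gives no algorithm.

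Noise and regression to the mean act on both randomised arms. A reader might infer that the comparison is biased in favour of one arm. It is not: both rates rise and a real difference may be diluted, but no direction is built in. The primary non-inferiority analysis is unaffected. What remains is a secondary comparison that ignores a known predictor and reports a p-value without an effect estimate.

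**What to change.** Keep the <9 definition in SAP 5.3.2. In the responder paragraph of SAP 4.2.2 and the notes to Tables 10.1.2.2.5.1 and 10.1.2.2.5.2, replace the chi-square or Fisher test for the LDQ responder with a logistic model containing treatment and baseline LDQ. Report the adjusted (standardised) difference in responder proportion, test minus control, with its 95% CI, beside the observed counts and percentages. Add a sentence that a non-significant p-value is not evidence of similarity. The by-age and by-region tables reuse the same shell and should follow.

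Optionally, show a version requiring a minimum fall from baseline, or <9 at both week 4 and week 8, as a sensitivity summary only. It should not replace the stated definition.

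Cost: SAP wording, two added shell rows and a little programming before database lock. No new data are needed and no stated definition changes.
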